5.2.2 Subsequent Cycles

Pregnancy Test: Every 6 weeks. After discontinuation from nivolumab these should be repeated at approximately 30 days and approximately 70 days.

Laboratory testing prior to each dose: Within 72 hrs prior to re-dosing to include CBC w/ differential, LFTs, BUN or serum urea level, creatinine, Ca, Mg, Na, K, Cl, LDH, Glucose, amylase, lipase, TSH (with reflexive Free T4 and Free T3)

System	Laboratory Value
Hematological	
Absolute neutrophil count (ANC)	$\geq 1500 / \text{mcL}$
Platelets	$\geq 100,000 / \text{mcL}$
Hemoglobin	$\geq 9 \text{ g/dL}$ or $\geq 5.6 \text{ mmol/L}$ without transfusion or EPO dependency (within 7 days of assessment)
Renal	
Serum creatinine OR Measured or calculated ^a creatinine clearance (GFR can also be used in place of creatinine or CrCl)	
$\leq \text{Serum creatinine} \leq 1.5 \times \text{ULN}$ or creatinine clearance (CrCl) $\geq 40 \text{ mL/min}$ (if using the Cockcroft-Gault formula below):
 
Female CrCl = $\frac{(140 - \text{age in years}) \times \text{weight in kg} \times 0.85}{72 \times \text{serum creatinine in mg/dL}}$
 
Male CrCl = $\frac{(140 - \text{age in years}) \times \text{weight in kg} \times 1.00}{72 \times \text{serum creatinine in mg/dL}}$

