5.2 Pre-Treatment Criteria

5.2.1 Cycle 1, Day 1

A serum or urine pregnancy testing is required within 72 hrs of study enrollment. Cycle 1, Day 1 labs will be used to confirm eligibility.

System	Laboratory Value
Hematological	
Absolute neutrophil count (ANC)	$\geq 1500 / \text{mcL}$
Platelets	$\geq 100,000 / \text{mcL}$
Hemoglobin	$\geq 9 \text{ g/dL}$ or $\geq 5.6 \text{ mmol/L}$ without transfusion or EPO dependency (within 7 days of assessment)
Renal	
Serum creatinine OR Measured or calculated ^a creatinine clearance (GFR can also be used in place of creatinine or CrCl)	$\leq \text{ Serum creatinine} \leq 1.5 \times \text{ULN}$ or creatinine clearance (CrCl) $\geq 40 \text{ mL/min}$ (if using the Cockcroft-Gault formula below): $\text{Female CrCl} = \frac{(140 - \text{age in years}) \times \text{weight in kg} \times 0.85}{72 \times \text{serum creatinine in mg/dL}}$ $\text{Male CrCl} = \frac{(140 - \text{age in years}) \times \text{weight in kg} \times 1.00}{72 \times \text{serum creatinine in mg/dL}}$
Hepatic	
Serum total bilirubin	$\leq 1.5 \times \text{ULN}$ OR
	Direct bilirubin $\leq \text{ULN}$ for subjects with total bilirubin levels $> 1.5 \text{ ULN}$
AST (SGOT) and ALT (SGPT)	$\leq 3 \text{ ULN}$ OR $\leq 5 \times \text{ULN}$ for subjects with liver metastases
Albumin	$\geq 2.5 \text{ mg/dL}$
Coagulation	
International Normalized Ratio	$\leq 1.5 \times \text{ULN}$ unless subject is receiving anticoagulant therapy

(INR) or Prothrombin Time (PT)	as long as PT or PTT is within therapeutic range of intended use of anticoagulants $\leq 1.5 \times \text{ULN}$ unless subject is receiving anticoagulant therapy
Activated Partial Thromboplastin Time (aPTT)	as long as PT or PTT is within therapeutic range of intended use of anticoagulants
^a Creatinine clearance should be calculated per institutional standard.	

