5.3 Agent Administration

For treatment schedule, see section 5.1

When study drugs (ipilimumab or nivolumab) are to be administered on the same day, separate infusion bags and filters must be used for each infusion. It is recommended that nivolumab be administered first. The second infusion will always be ipilimumab, and will start approximately 30 minutes after completion of the nivolumab infusion. The ipilimumab infusion will start no

SOONER than 30 minutes after completion of nivolumab infusion. An infusion window of +/- 10 minutes is allowed for both study drugs Nivolumab & Ipilimumab.

BMS-936558 (nivolumab) is to be administered as a 30 minute IV infusion. Ipilimumab should be administered as a 30 minute infusion following.

Ipilimumab and nivolumab may be diluted in 0.9% Sodium Chloride Solution or 5% Dextrose solution.

The dosing calculations should be based on the body weight. If the subject's weight on the day of dosing differs by > 5% from the weight used to calculate the dose, the dose must be recalculated. All doses should be rounded up or to the nearest milligram per institutional standard.

For the q3 week schedule, patients may be dosed no less than 18 days from the previous dose of drug; and dosed up to 3 days after the scheduled date if necessary.

For the q4 week schedule, patients may be dosed no less than 24 days from the previous dose of drug; and dosed up to 3 days after the scheduled date if necessary.

There will be no dose modifications permitted. Dose reductions or dose escalations are not permitted.

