Because of the potential for clinically meaningful nivolumab-related AEs requiring early recognition and prompt intervention, management algorithms have been developed for suspected AEs of selected categories. [see current Investigator Brochure for citation examples]

Dose delay criteria apply for all drug-related adverse events (regardless of whether or not the event is attributed to nivolumab, ipilimumab or both). All study drugs must be delayed until treatment can resume.

Nivolumab and ipilimumab administration should be delayed for the following:

- Any Grade ≥ 2 non-skin, drug-related adverse event, with the following exceptions:
 - Grade 2 drug-related fatigue or laboratory abnormalities do not require a treatment delay
- Any Grade 3 skin, drug-related adverse event
- Any Grade 3 drug-related laboratory abnormality, with the following exceptions for asymptomatic amylase or lipase, AST, ALT, or total bilirubin:
 - Grade 3 amylase or lipase abnormalities that are not associated with symptoms or clinical manifestations of pancreatitis do not require a dose delay. It is recommended to consult with the principle investigator for Grade 3 amylase or lipase abnormalities.
 - If a subject has a baseline AST, ALT, or total bilirubin that is within normal limits, delay dosing for drug-related Grade ≥ 2 toxicity
 - If a subject has baseline AST, ALT, or total bilirubin within the Grade 1 toxicity range, delay dosing for drug-related Grade ≥ 3 toxicity
- Any adverse event, laboratory abnormality, or intercurrent illness which, in the judgment of the investigator, warrants delaying the dose of study medication.

Criteria to Resume Treatment

Subjects may resume treatment with study drug when the drug-related AE(s) resolve to Grade ≤ 1 or baseline value, with the following exceptions:

- Subjects may resume treatment in the presence of Grade 2 fatigue
- Subjects who have not experienced a Grade 3 drug-related skin AE may resume treatment in the presence of Grade 2 skin toxicity
- Subjects with baseline Grade 1 AST/ALT or total bilirubin who require dose delays for reasons other than a 2-grade shift in AST/ALT or total bilirubin may resume treatment in the presence of Grade 2 AST/ALT OR total bilirubin
- Subjects with combined Grade 2 AST/ALT AND total bilirubin values meeting discontinuation parameters should have treatment permanently discontinued

- Drug-related pulmonary toxicity, diarrhea, or colitis, must have resolved to baseline before treatment is resumed

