- Drug-related endocrinopathies adequately controlled with only physiologic hormone replacement may resume treatment

If the criteria to resume treatment are met, the subject should restart treatment at the next scheduled timepoint per protocol. However, if the treatment is delayed past the next scheduled timepoint per protocol, the next scheduled timepoint will be delayed until dosing resumes. If treatment is delayed > 6 weeks, the subject must be permanently discontinued from study therapy, except as specified in discontinuation section.

Discontinuation Criteria

Treatment should be permanently discontinued for the following:

- Any Grade 2 drug-related uveitis or eye pain or blurred vision that does not respond to topical therapy and does not improve to Grade 1 severity within the re-treatment period OR requires systemic treatment
- Any Grade 3 non-skin, drug-related adverse event lasting > 7 days, with the following exceptions for drug-related laboratory abnormalities, uveitis, pneumonitis, bronchospasm, diarrhea, colitis, neurologic adverse event, hypersensitivity reactions, and infusion reactions
 - Grade 3 drug-related uveitis, pneumonitis, bronchospasm, colitis, neurologic adverse event, hypersensitivity reaction, or infusion reaction of any duration requires discontinuation
 - Grade 3 drug-related laboratory abnormalities do not require treatment discontinuation except those noted below
 - Grade 3 drug-related thrombocytopenia > 7 days or associated with bleeding requires discontinuation
 - Any drug-related liver function test (LFT) abnormality that meets the following criteria require discontinuation:
 - AST or ALT $> 8 \times$ ULN
 - Total bilirubin $> 5 \times$ ULN
 - Concurrent AST or ALT $> 3 \times$ ULN and total bilirubin $> 2 \times$ ULN
- Any Grade 4 drug-related adverse event or laboratory abnormality, except for the following events which do not require discontinuation:
 - Isolated Grade 4 amylase or lipase abnormalities that are not associated with symptoms or clinical manifestations of pancreatitis and decrease to $<$ Grade 4 within 1 week of onset.

- Isolated Grade 4 electrolyte imbalances/abnormalities that are not associated with clinical sequelae and are corrected with supplementation/appropriate management within 72 hours of their onset
- Any dosing interruption lasting > 6 weeks with the following exceptions:

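### The albumin eligibility limit is printed as ≥2.5 mg/dL in two tables, 1,000 times below 2.5 g/dL, so as written it excludes no one with low albumin

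*Combined protocol and SAP*

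**What the plan says.** **Albumin.** Table 1 in Section 3.1.5 defines adequate organ function for eligibility and gives the albumin minimum as 2.5 mg/dL. The table in Section 5.2.1 repeats the same figure and unit, and that section uses the Cycle 1 Day 1 laboratory results to confirm eligibility. Section 10 lists albumin among the serum chemistry tests, so a value will be on file for every patient. The Nursing Protocol Education Sheet refers staff to Table 1 and Section 5.2 for the criteria to treat.

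**Re-dosing.** Section 5.2.2 falls under the heading "5.2 Pre-Treatment Criteria". It has the line "Laboratory testing prior to each dose: Within 72 hrs prior to re-dosing to include CBC w/ differential" and lists ANC ≥1500/mcL, platelets ≥100,000/mcL and hemoglobin ≥9 g/dL, with no reference to grade or cause. Section 6 works by grade and attribution:

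- Scope: "Dose delay criteria apply for all drug-related adverse events".
- Exception: "Grade 2 drug-related fatigue or laboratory abnormalities do not require a treatment delay".
- Resumption: "Subjects may resume treatment with study drug when the drug-related AE(s) resolve to Grade ≤ 1 or baseline value", with listed exceptions, and then "If the criteria to resume treatment are met, the subject should restart treatment at the next scheduled timepoint per protocol".
- Discretion: a delay is also allowed for "Any adverse event, laboratory abnormality, or intercurrent illness which, in the judgment of the investigator, warrants delaying the dose of study medication".

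Section 5.3 adds: "Dose reductions or dose escalations are not permitted". Neither 5.2.2 nor Section 6 refers to the other. The nursing sheet's row on dose modifications and toxicity names Sections 5.2 and 6 together.

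**The concern.** A laboratory minimum in an eligibility table is a decision rule: a patient below it should not enter. At 2.5 mg/dL the albumin rule cannot do that job. A site following the text would admit patients whom the sponsor presumably meant to exclude. A site that silently reads the limit as 2.5 g/dL and turns away a patient at, say, 2.4 g/dL would be departing from the written criterion. Either way, an eligibility audit against the printed table gives the wrong answer. The consequence is for safety screening at entry and for the eligibility record, not for the statistical design.

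**Working it through.** **Albumin: inputs**

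- Printed limit: 2.5 mg/dL, in Table 1 (Section 3.1.5) and in the Section 5.2.1 table.
- Conversion: 1 g = 1,000 mg.
- Illustrative patient: albumin 1.5 g/dL. This value is an assumption for the example and is not in the documents.

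**Albumin: steps**

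1. Printed limit in g/dL: 2.5 / 1,000 = 0.0025 g/dL.
2. Ratio to the same number in g/dL: 2.5 / 0.0025 = 1,000.
3. Illustrative patient in the printed unit: 1.5 × 1,000 = 1,500 mg/dL.
4. Margin over the printed limit: 1,500 / 2.5 = 600. The patient passes. Under a limit of 2.5 g/dL the same patient fails, since 1.5 < 2.5.
5. Patients classified differently: anyone with albumin from 0.0025 g/dL up to, but not including, 2.5 g/dL passes as printed and would fail under g/dL. The documents give no albumin distribution, so the number of such patients among the planned 20 cannot be estimated.

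**Is g/dL the likely intent?** In the same table hemoglobin is given in g/dL. Apart from the albumin row, mg/dL appears there only for serum creatinine, in the clearance formula. A limit that no patient could plausibly miss has no reason to be in an eligibility table. This supports g/dL but does not prove it.

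**Can the re-dosing rules be followed together?** No arithmetic applies, so the two sections are compared directly.

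| Situation before a dose | Section 5.2.2 | Section 6 | Both met by |
|---|---|---|---|
| Counts at or above the minimums, no delay trigger | met | no delay | dosing |
| Counts at or above the minimums, delay trigger present | met | delay | holding |
| Count below a minimum, no graded delay trigger | not met | no delay required; investigator may delay | holding |
| Count below a minimum, delay trigger present | not met | delay | holding |

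In every row there is an action that complies with both sections. The Grade 2 exception removes a reason to delay. It does not authorise a dose below a pre-treatment minimum. The restart instruction is tied to the next time point under the protocol, and the protocol requires the 5.2.2 checks before each dose.

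**The case against.** **On albumin.** The strongest reply is that this is an obvious slip: any clinician would read 2.5 as g/dL, and nothing shows that a patient was or would be wrongly enrolled. It stands in part. The documents give no evidence of misenrolment, and the 1,000-fold and 600-fold figures are unit arithmetic, not an estimate of harm. But the same unit is printed in two operative tables, and a threshold that works only if staff correct it for themselves should be corrected in the text.

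**On re-dosing, a stronger reading is tempting.** A reader might infer that 5.2.2 and Section 6 contradict each other: a drug-related Grade 2 low count could fall below a 5.2.2 minimum while Section 6 requires no delay, or a resolved event could be directed to restart. With dose reductions barred, some staff would then hold and others dose. The documents do not support calling this an error, for three reasons.

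- The rules are compatible when applied together, and the nursing sheet names both sections in one row.
- No numeric conflict can be shown. Section 6 uses CTCAE version 4.0, whose cut-points are not printed. The no-delay limb would need Grade 3 to begin below the 5.2.2 minimum for the count in question. The restart limb would need a different assumption, that Grade 1 itself extends below the minimum. Return to baseline does not readily supply it, because the same count minimums apply at entry and at Cycle 1 Day 1.
- The available count of decisions is not a count of affected decisions. In weeks 1 to 12, the Q3W schedule gives 4 − 1 = 3 re-dosing decisions per patient and the Q2W nivolumab schedule gives 6 − 1 = 5. For 20 patients that is 3 × 20 = 60 to 5 × 20 = 100 if nobody stops treatment. Only decisions with a low count could matter. The documents give no rate for these, and the most frequent drug-related events listed in Section 2.2.3 include no cytopenia or anemia.

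What remains is that no sentence states how the two sections combine. The 5.2.2 table also appears to be incomplete: it calls for liver tests but shows no hepatic rows. Nothing should be concluded from what it omits, including albumin.

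**Conclusion.** The albumin limit is wrong as written in Sections 3.1.5 and 5.2.1. The printed minimum is 0.0025 g/dL and screens out no one with low albumin. Severity is minor. Two things are inferred: that the number 2.5 is right and that g/dL was the intended unit. If the sponsor meant another value, the number needs correcting as well as the unit. The practical effect ranges from none, if all staff already read the limit as g/dL, to admission of every otherwise eligible patient below 2.5 g/dL. The documents do not allow a figure within that range.

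The relation between 5.2.2 and Section 6 is an optional clarification, not an error. No effect on OS3, the sample size or the error rates is claimed for either item.

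**What to change.** 1. Change the albumin limit to ≥2.5 g/dL in Table 1 (Section 3.1.5) and in the Section 5.2.1 table, after the sponsor confirms the intended value.
2. Optionally, add one sentence to Section 6: the pre-dose minimums in Section 5.2.2 apply in addition to the delay and resumption criteria, and the dose is held if either is not met. This would also make clear that the minimums cover low counts not attributed to study drug, for which Section 6 otherwise relies on investigator judgment.

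The cost is one unit correction in two tables and, if wanted, one sentence. No extra procedures, patients or analyses are needed.

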5.3 Agent Administration

For treatment schedule, see section 5.1

When study drugs (ipilimumab or nivolumab) are to be administered on the same day, separate infusion bags and filters must be used for each infusion. It is recommended that nivolumab be administered first. The second infusion will always be ipilimumab, and will start approximately 30 minutes after completion of the nivolumab infusion. The ipilimumab infusion will start no

SOONER than 30 minutes after completion of nivolumab infusion. An infusion window of +/- 10 minutes is allowed for both study drugs Nivolumab & Ipilimumab.

BMS-936558 (nivolumab) is to be administered as a 30 minute IV infusion. Ipilimumab should be administered as a 30 minute infusion following.

Ipilimumab and nivolumab may be diluted in 0.9% Sodium Chloride Solution or 5% Dextrose solution.

The dosing calculations should be based on the body weight. If the subject's weight on the day of dosing differs by > 5% from the weight used to calculate the dose, the dose must be recalculated. All doses should be rounded up or to the nearest milligram per institutional standard.

For the q3 week schedule, patients may be dosed no less than 18 days from the previous dose of drug; and dosed up to 3 days after the scheduled date if necessary.

For the q4 week schedule, patients may be dosed no less than 24 days from the previous dose of drug; and dosed up to 3 days after the scheduled date if necessary.

There will be no dose modifications permitted. Dose reductions or dose escalations are not permitted.

5.4 General Concomitant Medication and Supportive Care Guidelines

Antiemetic premedications should not be routinely administered prior to dosing of drugs. See Section 6 for premedication recommendations following a nivolumab or ipilimumab related infusion reaction.

Note: Radiation therapy to a symptomatic single extracranial site and/or one intracranial site may be allowed at the investigator's discretion, as long as ipilimumab is held during radiation and at least 3 weeks after completion of radiation.

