11.1.2 Disease Parameters

Measurable disease. Measurable lesions are defined as those that can be accurately measured in at least one dimension (longest diameter to be recorded) as ≥ 20 mm by chest x-ray or ≥ 10 mm with CT scan, MRI, or calipers by clinical exam. All tumor measurements must be recorded in millimeters (or decimal fractions of centimeters).

Note: Tumor lesions that are situated in a previously irradiated area might or might not be considered measurable.

Malignant lymph nodes. To be considered pathologically enlarged and measurable, a lymph node must be ≥ 15 mm in short axis when assessed by CT scan (CT scan slice thickness recommended to be no greater than 5 mm). At baseline and in follow-up, only the short axis will be measured and followed.

Non-measurable disease. All other lesions (or sites of disease), including small lesions (longest diameter <10 mm or pathological lymph nodes with ≥ 10 to <15 mm short axis), are considered non-measurable disease. Bone lesions, leptomeningeal disease, ascites, pleural/pericardial effusions, lymphangitis cutis/pulmonitis, inflammatory breast disease, abdominal masses (not followed by CT or MRI), and cystic lesions are all considered non-measurable.

Note: Cystic lesions that meet the criteria for radiographically defined simple cysts should not be considered as malignant lesions (neither measurable nor non-measurable) since they are, by definition, simple cysts.

‘Cystic lesions’ thought to represent cystic metastases can be considered as measurable lesions, if they meet the definition of measurability described above. However, if non-cystic lesions are present in the same participant, these are preferred for selection as target lesions.

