11.1.4 Response Criteria

11.1.4.1 Evaluation of Target Lesions

Complete Response (CR): Disappearance of all target lesions. Any pathological lymph nodes (whether target or non-target) must have reduction in short axis to <10 mm.

Partial Response (PR): At least a 30% decrease in the sum of the diameters of target lesions, taking as reference the baseline sum diameters.

Progressive Disease (PD): At least a 20% increase in the sum of the diameters of target lesions, taking as reference the smallest sum on study (this includes the baseline sum if that is the smallest on study). In addition to the relative increase of 20%, the sum must also demonstrate an absolute increase of at least 5 mm. (Note: the appearance of one or more new lesions is also considered progressions).

Stable Disease (SD): Neither sufficient shrinkage to qualify for PR nor sufficient increase to qualify for PD, taking as reference the smallest sum diameters while on study.

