11.2.4 Response Criteria

11.2.4.1 Evaluation of Intracranial Lesions

Complete Response (CR): Requires all of the following:

- complete disappearance of all enhancing measurable and nonmeasurable disease sustained for at least 4 weeks
- no new lesions
- stable or decreasing corticosteroids (the steroid dose at the time of the scan evaluation should be no greater than the dose at time of baseline scan)
- stable or improved clinically

Participants with non-measurable disease cannot have a complete response. The best possible response is stable disease.

Partial Response (PR): All of the following criteria must be met:

- Greater than or equal to 50% decrease compared to baseline in the sum of products of perpendicular diameters of all measurable enhancing lesions sustained for at least 4 weeks. In the absence of a confirming scan 4 weeks later, this scan will be considered only stable disease.
- no progression of non-measurable disease.
- no new lesions
- stable or reduced corticosteroid dose (the steroid dose at the time of the scan evaluation should be no greater than the dose at time of baseline scan)
- stable or improved clinically

Progressive Disease (PD): At least one of the following must be true:

- $\geq 25\%$ increase in the sum of products of all measurable lesions over smallest sum observed (over baseline if no decrease) using the same techniques as baseline
- clear worsening of any nonmeasurable disease*
- appearance of any new enhancing lesion/site
- clear clinical worsening (unless clearly unrelated to this cancer, e.g. seizures, medication side effects, complications of therapy, cerebrovascular events, infection)
- failure to return for evaluation due to death or deteriorating condition

* Progression of non-measurable CNS lesions is defined as follows:

- a lesion initially at baseline $\leq 5\text{mm}$ in diameter that increases to $\geq 10\text{mm}$ in diameter, or
- a lesion initially at baseline 6-9 mm in diameter that increases by at least 5 mm in diameter.

Stable Disease (SD): All of the following criteria must be met:

- Does not qualify for CR, PR or progression
- All measurable and non-measurable sites must be assessed using the same techniques as baseline
- Stable clinically.

A summary of the response criteria is in the below:

	Complete Response	Partial Response	Stable Disease	Progressive Disease
T1-Gd+	None	$\geq 50\%$ decrease	$<50\%$ decrease- $<25\%$ increase	$\geq 25\%$ increase*
New Lesion	None	None	None	Present*

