APPENDIX B

TUMOR ASSESSMENT PER IMMUNE-RELATED RESPONSE CRITERIA

Immune-related Response Criteria (irRC) are derived from modified World Health Organization (mWHO) conventions. Assessments of lymph nodes are derived from current RECIST guidelines.

Definitions of Measurable/non-Measurable Lesions

All measurable and non-measurable lesions should be assessed at Screening and at the defined tumor assessment time points. Additional assessments may be performed, as clinically indicated for suspicion of progression.

Measurable Lesions

Measurable lesions are lesions that can be accurately measured in 2 perpendicular diameters, with at least 1 diameter ≥ 20 mm and the other dimension ≥ 10 mm (10 mm x 10 mm for spiral CT with cuts of 5 mm). The area will be defined as the product of the largest diameter with its perpendicular.

Lymph nodes may also be considered measurable. To be considered pathologically enlarged and measurable, a lymph node must be at least 15 mm in short axis when assessed by CT scan (CT scan slice thickness recommended to be no greater than 5 mm).

Non-Measurable Lesions

Non-measurable (evaluable) lesions are all other lesions, including unidimensional measurable disease and small lesions (lesions without at least 1 diameter ≥ 20 mm, or pathological lymph nodes with short axis $\square 15$ mm), and any of the following: lesions occurring in a previously irradiated area (unless they are documented as new lesions since the completion of radiation therapy), bone lesions, leptomeningeal disease, ascites, pleural or pericardial effusion, lymphangitis cutis/pulmonis, abdominal masses that are not pathologically/cytologically confirmed and followed by imaging techniques and cystic lesions. Lymph nodes that have a short axis < 10 mm are considered non-pathological and should not be recorded or followed.

Definitions of Index/non-Index Lesions

Index Lesions

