Measurable lesions, up to a maximum of 5 lesions per organ and ten lesions in total, must be identified as index lesions to be measured at Screening. The index lesions should be representative of all involved organs. In addition, index lesions must be selected based on their size (eg, lesions with the longest diameters), their suitability for accurate repeat assessment by imaging techniques, and how representative they are of the subject's tumor burden. At Screening, a Sum of the Product Diameters (SPD) for all index lesions will be calculated and considered the baseline SPD. The baseline sum will be used as the reference point to determine the objective tumor response of the index lesions at tumor assessment.

Non Index Lesions

Measurable lesions, other than index lesions, and all sites of non-measurable disease, will be identified as non-index lesions. Non-index lesions will be evaluated at the same assessment time

points as the index lesions. In subsequent assessments, changes in non-index lesions will contribute only in the assessment of complete response.

Calculation of Sum of Product of Diameters (SPD)

Sum of Product of Diameters is an estimate of tumor burden. The 2 greatest perpendicular diameters are used to estimate the size of each tumor lesion. The SPD is calculated as the sum of the product of the diameters for index tumor lesions. Several variations of the SPD are identified for the purpose of classification of tumor responses.

SPD at Baseline: The sum of the product of the diameters for all index lesions identified at baseline prior to treatment on Day 1.

SPD at tumor assessment: For every on-study tumor assessment collected per protocol or as clinically indicated, the SPD at tumor assessment will be calculated using tumor imaging scans. All index lesions and all new measurable lesions that have emerged after baseline will contribute to the SPD at tumor assessment (irSPD).

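### A target lesion irradiated during the study stays in the response sums, so radiation shrinkage can be scored as a complete or partial response

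*Combined protocol and SAP*

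**What the plan says.** Section 5.4 permits radiation during protocol therapy: "Radiation therapy to a symptomatic single extracranial site and/or one intracranial site may be allowed". The choice is left to the investigator, on condition that ipilimumab is withheld over that period and for a minimum of 3 weeks afterwards. The ipilimumab hold shows that the patient is still on study treatment. The section says nothing about response assessment afterwards.

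Response is scored against lesions chosen before treatment:

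- **Intracranial (RANO, 11.2.4.1).** PR requires "Greater than or equal to 50% decrease compared to baseline in the sum of products of perpendicular diameters of all measurable enhancing lesions", sustained for 4 weeks, with no new lesion, no rise in steroid dose above baseline and no clinical decline.
- **Extracranial (RECIST, 11.1.4.1).** PR requires "At least a 30% decrease in the sum of the diameters of target lesions, taking as reference the baseline sum diameters". Section 11.1.2 has target lesions identified and measured at baseline.
- **Extracranial (irRC, Appendix B).** PR requires a fall of at least 50% in the sum of products. "At Screening, a Sum of the Product Diameters (SPD) for all index lesions will be calculated and considered the baseline SPD".

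Irradiated lesions are mentioned twice, both times under measurability. Section 11.1.2 notes: "Tumor lesions that are situated in a previously irradiated area might or might not be considered measurable". Appendix B lists among non-measurable disease "lesions occurring in a previously irradiated area (unless they are documented as new lesions since the completion of radiation therapy"). The intracranial definitions in Section 11.2.2 do not mention them.

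Section 13.6 reports intracranial and extracranial response as proportions with 90% exact binomial intervals. For intracranial response it gives a maximum width of 0.42 at 18 patients.

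**The concern.** The response rates are meant to describe the activity of nivolumab plus ipilimumab. If a target lesion is irradiated after baseline and shrinks, that shrinkage enters the sum like any other, and a reader following the criteria as written would record it as drug response. There is no control arm against which to judge how much of the rate comes from radiation. The error runs one way: it can add responders but not remove them. Section 2.1 itself credits radiotherapy, together with intrathecal chemotherapy, with local control, so the mechanism is one the protocol recognises.

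For lesions irradiated before entry the three criteria also differ. RECIST leaves the matter open, irRC excludes them unless new since radiation, and RANO is silent. Section 13.6 plans to document disagreements between RECIST and irRC; some could arise from this mismatch alone.

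**Working it through.** **1. The plan's own figure.** The Clopper-Pearson 90% interval for k responders of 18, over k = 0 to 18, is widest at k = 9: 0.291 to 0.709, a width of 0.418. This reproduces the stated 0.42.

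**2. When one irradiated lesion is enough.** If the lesion carries share s of the baseline sum, shrinks by fraction f, and nothing else changes, the sum falls by s × f. PR needs s × f ≥ 0.30 (RECIST) or ≥ 0.50 (RANO and irRC products). With m equal-sized lesions and complete disappearance of one, the fall is 1/m:

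| m | Fall | RECIST 30% | 50% product threshold |
|---|---|---|---|
| 1 | 100% | met | met |
| 2 | 50% | met | met |
| 3 | 33% | met | not met |
| 4 | 25% | not met | not met |
| 5 | 20% | not met | not met |

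**3. Worked cases with a dominant lesion (assumed sizes).**

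- RANO: lesions of 20 × 20 and 10 × 10 mm give 400 + 100 = 500. If the irradiated larger lesion falls to 10 × 10 and the other is unchanged, the sum is 200. Change: (200 − 500)/500 = −60%, which meets the PR size threshold. Without the irradiated lesion the sum is 100 before and after: 0%.
- RECIST: lesions of 40 and 20 mm give 60. If the irradiated 40 mm lesion falls to 20 mm, the sum is 40. Change: (40 − 60)/60 = −33%, a PR. Without it, 20 before and after: 0%.

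**4. Effect on the rate.** One patient of 18 is 1/18 = 5.6 points. The number irradiated is not in the documents, so the table assumes 4 scored responders and shows the result if 0 to 3 of them were due to radiation:

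| Radiation-driven | Remaining responders | Rate | 90% exact interval |
|---|---|---|---|
| 0 | 4/18 | 22.2% | 8.0–43.9% |
| 1 | 3/18 | 16.7% | 4.7–37.7% |
| 2 | 2/18 | 11.1% | 2.0–31.0% |
| 3 | 1/18 | 5.6% | 0.3–23.8% |

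Section 11.2.1 limits intracranial evaluability to patients with measurable CNS disease, so the denominator may be below 18. With 12 or 9 evaluable patients (assumed), one patient is 8.3 or 11.1 points.

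**5. Expected inflation (illustration).** Let p be the true drug response rate, q the fraction irradiated, and h the fraction of irradiated non-responders who reach PR through radiation, with irradiation unrelated to drug response. Scored rate = p + (1 − p) × q × h. With p = 10% and q from 10% to 30%:

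- h = 0.5: 0.10 + 0.90 × 0.10 × 0.5 = 14.5%, up to 0.10 + 0.90 × 0.30 × 0.5 = 23.5%.
- h = 1: 0.10 + 0.90 × 0.10 = 19%, up to 0.10 + 0.90 × 0.30 = 37%.

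**6. Do the irradiated-area texts close the gap?** Both say which lesions count as measurable. Target lesions are set at baseline and index lesions at Screening, before any on-study radiation. No text reclassifies a chosen lesion when it is irradiated later.

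**The case against.** The strongest case against is that the path to a false response is narrow and partly guarded. That is largely right, and it limits the point in four ways.

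- **Share of the sum.** The treated lesion must be a target and carry much of the total. Section 11.1.2 classes bone lesions and leptomeningeal disease as non-measurable, so radiation there cannot move a target sum. A reader might infer that symptomatic sites are usually the largest targets; nothing in the documents says so.
- **Progression first.** Under RANO, definite clinical worsening or a new lesion is progression, and Section 11.2.4.2 stops recording best response there. Where worsening CNS symptoms prompt the radiation, later shrinkage may not count. This does not cover a lesion irradiated without worsening, and RECIST target-lesion progression has no symptom criterion.
- **Confirmation and central review.** The RANO 4-week requirement shows that a fall lasts, not what caused it. Central review (Section 11.3) applies the same criteria.
- **Recoverability.** A reader might infer that radiation and drug effects can never be separated afterwards. That goes too far. Lesions are measured and scans centrally reviewed, so an analysis without the irradiated lesion is feasible if site and date are recorded. What is missing is a rule fixed in advance.

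A reader might also infer that Section 11.4 counts any radiographic or neurologic improvement as leptomeningeal response. Its PR row also has a cytologic criterion, and its radiographic cell rules out new CNS sites. The table does not say how the columns combine, but that is a separate matter, and no leptomeningeal inflation has been shown here.

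**Conclusion.** The point holds in a limited form. On-study radiation is allowed, and no response rule removes a target lesion irradiated after baseline, so its shrinkage can produce a scored CR or PR. It does not follow that every irradiated patient becomes a responder: the lesion must carry enough of the sum, progression must not have been scored first, and under RANO the fall must last and the steroid and clinical conditions must be met.

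The bias is upward in the secondary intracranial and extracranial response rates, at 5.6 points per such patient out of 18 and more with fewer evaluable patients. The total cannot be stated, because the documents give no frequency of on-study radiation; the multi-patient figures rest on assumed counts.

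A reader might carry this over to the primary result. The documents do not support that: 3-month survival is scored on vital status, and neither the Simon rule nor any other decision rule uses response. This is a correction the plan should make, not a threat to its main conclusion.

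**What to change.** In Sections 11.1.4 and 11.2.4 and Appendix B, state that:

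- from the date of on-study radiation, the irradiated lesion cannot contribute to CR or PR, and baseline and later sums used for response are recalculated without it;
- responses documented before radiation stand;
- a patient whose only target lesion in a compartment is irradiated before response stays in the denominator as a non-responder there, with a sensitivity analysis treating such patients as not evaluable.

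The text should also say whether later growth of that lesion counts toward progression, since the rule above covers response only.

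In Section 11.4, state that radiographic improvement confined to an irradiated site does not by itself support a leptomeningeal response. Record radiation site and date on the response form. For lesions irradiated before entry, reconcile Sections 11.1.2 and 11.2.2 and Appendix B into one rule; which rule is for the study team to choose.

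The cost is a few sentences and a small addition to one form. With irradiated patients kept in the denominator, the maximum interval width at 18 patients stays 0.42. The downside is that an occasional true drug response in an irradiated lesion goes uncredited, so the reported rate may be slightly low; the sensitivity analysis shows how much depends on the non-responder rule. Whether radiation is permitted does not change.
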